4.2. Inclusion Criteria

Subjects must meet **all** of the following inclusion criteria to be eligible for participation in this study.

- 1) The ability to understand and sign a written informed consent form, which must be obtained prior to initiation of study procedures
- 2) Non-pregnant/non-lactating females, ≥ 18 years of age at Screening
- 3) Plasma HIV-1 RNA ≥ 500 copies/mL at Screening Visit
- 4) Currently taking a failing ARV regimen that contains 2 NRTIs and an NNRTI
- 5) No prior or current ARV regimens containing integrase inhibitor (INSTI) or protease inhibitor (PI)
- 6) Screening genotype must show at least the following resistance mutation profile (a local genotype (within 3 months of the Screening visit) is acceptable for enrollment upon review by the Sponsor):
 - a) K65R or at least 3 TAMS (defined as: M41L, D67N, K70R, L210W, T215F/Y or K219Q/E/N/R) or Q151M
 - b) and at least one primary resistance mutation to an NNRTI (defined as L100I, K101E/P, K103N/R/S, V106M/A, V108I, E138A/G/K/Q/R, V179L, Y181C/I/V, Y188C/H/L, G190A/E/Q/S, H221Y, P225H, F227C or M230L/I)
- 7) Adequate renal function:

Estimated glomerular filtration rate ≥ 70 mL/min according to the Cockcroft-Gault formula for creatinine clearance {[Cockcroft 1976](#)}:

 - Female:
$$\frac{(140 - \text{age in years}) \times (\text{wt in kg}) \times 0.85}{72 \times (\text{serum creatinine in mg/dL})} = \text{CLcr (mL/min)}$$
$$\frac{(140 - \text{age in years}) \times (\text{wt in kg})}{72 \times (\text{serum creatinine in } \mu\text{mol/L}) \times 0.6786} = \text{CLcr (mL/sec)}$$

- 8) Normal ECG (or if abnormal, determined by the Investigator to be not clinically significant)
- 9) CD4 > 100 cells/ μ L
- 10) Hepatic transaminases (AST and ALT) $\leq 2 \times$ upper limit of normal (ULN)
- 11) Total bilirubin ≤ 1.5 mg/dL (≤ 26 μ mol/L), or normal direct bilirubin
- 12) Adequate hematologic function (absolute neutrophil count $\geq 750/\text{mm}^3$ (≥ 0.75 GI/L); platelets $\geq 50,000/\text{mm}^3$ (≥ 50 GI/L); hemoglobin ≥ 10 g/dL (≥ 100 g/L))
- 13) Serum amylase $\leq 2 \times$ ULN (subjects with serum amylase $> 2 \times$ ULN will remain eligible if serum lipase is $\leq 2 \times$ ULN)

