6.8.1. Blood Samples

- **Blood samples will be collected for the following laboratory analyses** (Refer to Appendix 2, and Appendix 3):
 - Serum pregnancy test (females of childbearing potential only). If the test is positive, the subject will not be enrolled (**Screening and Day 1 only**). Positive urine pregnancy tests will be confirmed with a serum test.
 - Follicle-stimulating hormone (FSH) (females who have ceased menstruating for greater than or equal to 12 months but do not have documentation of ovarian hormonal failure) Female subject post-menopausal for less than two year, if FSH < 40 mIU/ mL a serum pregnancy test will be required (**Screening only**)
 - Chemistry profile: alkaline phosphatase, AST, ALT, total bilirubin, direct and indirect bilirubin, total protein, albumin, CPK, bicarbonate, blood urea nitrogen (BUN), calcium, chloride, creatinine, glucose, phosphorus, magnesium, potassium, sodium, uric acid, amylase (reflex lipase testing is performed in subjects with total amylase > 1.5 × ULN)
 - Metabolic profile: Fasting (no food or drinks, except water, at least 8 hours prior to blood collection) glucose and lipid panel (total cholesterol, HDL, direct LDL, and triglycerides) collected at **Part 1 – Day 1, Part 2 – Day 1, Weeks 12** CCI [REDACTED].
 - If the subject has not fasted prior to the visit, the visit may proceed, but the subject must return within 72 hours in a fasted state to draw blood for the metabolic assessments

— eGFR according to the Cockcroft-Gault formula:

$$\text{Female: } \frac{(140 - \text{age in years}) \times (\text{wt in kg}) \times 0.85}{72 \times (\text{serum creatinine in mg/dL})} = \text{CLcr (mL/min)}$$

$$\frac{(140 - \text{age in years}) \times (\text{wt in kg})}{72 \times (\text{serum creatinine in } \mu\text{mol/L})} \times 0.85 = \text{CLcr (mL/sec)}$$

— Hematology profile: complete blood count (CBC) with differential and platelet count.

— CD4 cell count and percentage

— Plasma HIV-1 RNA

— HBV blood panel: Hepatitis B virus surface antigen serology (HBsAg), Hepatitis B virus surface antibody (HBsAb) and Hepatitis B virus core antibody (HBcAb)

The following tests will be conducted by the central laboratory if the following criteria are met:

- If positive HBsAg, reflex testing for plasma HBV DNA, Hepatitis B virus e-antigen (HBeAg) (if negative, reflex Hepatitis B virus e-Antibody [HBeAb]), and quantitative HBsAg.

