8.3. Data Handling Conventions

HIV-1 RNA results of “No HIV-1 RNA detected” and “< 20 cp/mL HIV-1 RNA Detected” will be imputed as 19 copies/mL for analysis purposes.

Natural logarithmic transformation of plasma concentrations and PK parameters will be applied for PK analysis.

Laboratory data that are continuous in nature but are less than the lower limit of quantitation or above the upper limit of quantitation will be imputed to the value of the lower or upper limit plus or minus one significant digit, respectively (e.g., if the result of a continuous laboratory test is < 20, a value of 19 will be assigned).

Missing data can have an impact upon the interpretation of the trial data. In general, values for missing data will not be imputed. However, a missing pre-treatment laboratory result would be treated as normal (i.e., no toxicity grade) for the laboratory abnormality summary.

All available data for subjects that do not complete the study will be included in data listings.

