### 7.2.2.1. Treatment Emergent Laboratory Abnormalities

Treatment-emergent laboratory abnormalities are defined as values that increase at least 1 toxicity grade from predose at any posedose time point, up to 30 days after Part 1 last dose date or before Part 2 first dose date (if applicable), whichever occurs earlier. If the relevant predose laboratory value is missing, any abnormality of at least Grade 1 observed within the time frame specified above will be considered treatment-emergent.

Fasting glucose and nonfasting glucose (including glucose results without a known fasting status) are graded based on different grading scales as specified in the protocol.

Treatment-emergent laboratory abnormalities will be summarized for fasting glucose. Maximum postdose grade, instead of treatment-emergent grade, for nonfasting glucose (including glucose results without a known fasting status) will be summarized, as nonfasting glucose was not assessed at predose visit for most of the subjects; therefore, an abnormality is treatment-emergent or not cannot be determined for these subjects.

Both urine RBC based on microscopic examination, labeled as Hematuria (Quantitative), and urine blood based on dipstick, labeled as Hematuria (Dipstick), are assessed routinely and assigned a toxicity grade in this study. Urine RBC based on microscopic examination will be presented in laboratory toxicity summary tables and listings while urine blood based on dipstick will be presented in the listings only.

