### 7.2.2.2. Summaries of Laboratory Abnormalities

Laboratory data that are categorical will be summarized using the number and percentage of subjects in the study with the given response at predose and each scheduled postdose time point.

The following summaries (number and percentage of subjects) for treatment-emergent laboratory abnormalities will be provided by lab test and cohort; subjects will be categorized according to the most severe postdose abnormality grade for a given lab test:

- Treatment-emergent laboratory abnormalities
- Treatment-emergent Grade 3 and 4 laboratory abnormalities
- Treatment-emergent Grade 2, 3, and 4 laboratory abnormalities

For all summaries of laboratory abnormalities, the denominator is the number of subjects with any nonmissing postdose values up to the minimum of (1) 30 days after Part 1 last dose date, and (2) Part 2 first dose date (if applicable).

A by-subject listing of all treatment-emergent laboratory abnormalities and treatment-emergent Grade 3 or 4 laboratory abnormalities will be provided by subject ID number and visit in chronological order. This listing will include all test results that were collected throughout the study (including Part 2) for the lab test of interest, with all applicable severity grade displayed.

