### 7. Graded Laboratory Abnormalities Summary

The following labels will be used for treatment-emergent laboratory abnormalities and treatment-emergent Grade 3 or 4 laboratory abnormalities summary tables and listings:

Battery	Lab Test Label Used in l-labtox Listing	Toxicity Direction	Lab Test Label Used in t-labtox Table
Hematology	Hemoglobin	Decrease	Hemoglobin (Decreased)
	Neutrophils	Decrease	Neutrophils (Decreased)
	Platelets	Decrease	Platelets (Decreased)
	WBC	Decrease	WBC (Decreased)
Chemistry	Albumin	Decrease	Albumin (Decreased)
	Alkaline Phosphatase	Increase	Alkaline Phosphatase (Increased)
	ALT	Increase	ALT (Increased)
	Amylase	Increase	Amylase (Increased)
	AST	Increase	AST (Increased)
	Bicarbonate	Decrease	Bicarbonate (Decreased)
	Corrected Calcium	Increase	Corrected Calcium (Hypercalcemia)
	Corrected Calcium	Decrease	Corrected Calcium (Hypocalcemia)
	Creatine Kinase (CK)	Increase	Creatine Kinase (Increased)
	Creatinine	Increase	Creatinine (Increased)
	GGT	Increase	GGT (Increased)
	Lipase	Increase	Lipase (Increased)
	Magnesium	Decrease	Magnesium (Hypomagnesemia)
	Phosphate	Decrease	Phosphate (Hypophosphatemia)
	Serum Glucose (Fasting)	Increase	Serum Glucose (Fasting, Hyperglycemia)
	Serum Glucose (Fasting)	Decrease	Serum Glucose (Fasting, Hypoglycemia)

Battery	Lab Test Label Used in l-labtox Listing	Toxicity Direction	Lab Test Label Used in t-labtox Table
	Serum Glucose (Nonfasting)	Increase	Serum Glucose (Nonfasting, Hyperglycemia)
	Serum Glucose (Nonfasting)	Decrease	Serum Glucose (Nonfasting, Hypoglycemia)
	Serum Potassium	Increase	Serum Potassium (Hyperkalemia)
	Serum Potassium	Decrease	Serum Potassium (Hypokalemia)
	Serum Sodium	Increase	Serum Sodium (Hypernatremia)
	Serum Sodium	Decrease	Serum Sodium (Hyponatremia)
	Total Bilirubin	Increase	Total Bilirubin (Hyperbilirubinemia)
	Total Cholesterol (Fasting)	Increase	Total Cholesterol (Fasting, Hypercholesterolemia)
	Triglycerides (Fasting)	Increase	Triglycerides (Fasting, Increased)
	LDL (Fasting)	Increase	LDL (Fasting, Increased)
	Urea Nitrogen (BUN)	Increase	Urea Nitrogen (Increased)
	Uric Acid	Increase	Uric Acid (Hyperuricemia)
	Uric Acid	Decrease	Uric Acid (Hypouricemia)
	Prothrombin Intl. Normalized Ratio (INR)	Increase	N/A
	Prothrombin Time (PT)	Increase	N/A
Urinalysis	Urine Blood	Increase	N/A
	Urine Glucose	Increase	Urine Glucose (Glycosuria)
	Urine Protein	Increase	Urine Protein (Proteinuria)
	Urine RBC	Increase	Urine RBC (Hematuria, Quantitative)

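### Lipase is measured only as a reflex to raised amylase, yet the SAP tabulates it as treatment-emergent under rules written for routinely drawn tests

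*SAP*

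**What the plan says.** Protocol 6.8.1 includes amylase in the chemistry profile and makes lipase conditional on it: "reflex lipase testing is performed in subjects with total amylase > 1.5 × ULN". No scheduled lipase draw is described.

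SAP Appendix 3 item 7 nevertheless gives lipase, in the increased direction, a label in both the listing and the treatment-emergent summary table. Two general rules then apply to that row.

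- **Missing predose value.** SAP 7.2.2.1: "If the relevant predose laboratory value is missing, any abnormality of at least Grade 1" seen in the Part 1 postdose window is classed as treatment-emergent. Protocol 8.6.3 has the same rule, and Protocol 8.3 states that "a missing pre-treatment laboratory result would be treated as normal".
- **Denominator.** SAP 7.2.2.2 says the summaries "will be provided by lab test and cohort" and that "the denominator is the number of subjects with any nonmissing postdose values" in the Part 1 window. It does not say whether those values must be for the test in question.

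On entry, Protocol 4.2 inclusion criterion 13 accepts amylase up to 2 × ULN without reference to lipase. A subject above that "will remain eligible if serum lipase is" no more than 2 × ULN.

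The SAP departs from its general rules for some other tests. For nonfasting glucose, 7.2.2.1 and Appendix 3 item 6 say that emergence cannot be determined, because most subjects had no predose measurement, and 7.2.2.1 summarises maximum postdose grade instead. INR and prothrombin time are listed but not tabulated. Lipase has no such exception.

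**The concern.** For a routinely drawn test, a missing predose value is an accident and a rule that errs towards flagging is reasonable. For a reflex test the gap is built in. A subject with amylase at or below 1.5 × ULN before dosing has no protocol-specified lipase at that time. If her amylase later passes the threshold, the first lipase she ever has is postdose, and any value above 1.0 × ULN (Grade 1 in Protocol Appendix 5) is labelled emergent. Entry does not rule out a pre-existing rise, since criterion 13 looks at lipase only when amylase is above 2 × ULN.

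The denominator raises a second question. If it means subjects with a postdose lipase, the group has been selected for Grade 2 or higher amylase, and its percentage would stand beside rows such as amylase that come from the routine chemistry profile.

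What is at stake is how one row is read. The final analysis covers only the two open-label sentinel cohorts, so no placebo arm would expose a spurious rate. Protocol 1.8.1 says no clinical safety data were available for the 180 mg dose.

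**Working it through.** The documents state no lipase rate and no count of reflex tests, so there is no figure of the plan's own to reproduce. The check follows the rules through and sizes the result on assumed counts.

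**Inputs.** Reflex threshold: amylase above 1.5 × ULN (Protocol 6.8.1). Lipase Grade 1: above 1.0 to 1.5 × ULN (Protocol Appendix 5). Cohort size *N*: 11 in Sentinel Cohort 1 (Protocol 1.2.3.3.1.1) and up to 10 in Sentinel Cohort 2 (SAP 1.2). Number with a postdose lipase, *T*: not given; 1 to 4 per cohort assumed. Number with a raised postdose lipase, *x*: not given; 1 assumed.

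**Step 1. What happens to each kind of subject.**

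| Predose amylase | Postdose amylase | Predose lipase | Postdose lipase | When flagged as emergent |
|---|---|---|---|---|
| never above 1.5 × ULN | above 1.5 × ULN | none specified | yes | any Grade 1 or higher |
| above 1.5 × ULN at Screening or Day 1 | above 1.5 × ULN | yes | yes | only if the grade increases |
| any | never above 1.5 × ULN | either | none | never |

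The second row follows because SAP 3.8.1 takes the last available value before first dose as predose, so a Screening reflex result counts. The defect lies in the first row only.

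**Step 2. Share flagged by the rule alone.** Let *q* be the share of raised postdose lipase values that come from subjects with a predose lipase. The share labelled emergent only because predose is missing is 1 − *q*: 100% at *q* = 0, 50% at *q* = 0.5 and 0% at *q* = 1. The documents do not give *q*.

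**Step 3. Denominator read per test.** The table would show *x*/*T* against a whole-cohort *x*/*N*. The ratio is (*x*/*T*) ÷ (*x*/*N*) = *N*/*T*, whatever *x* is. With *x* = 1:

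| *T* | 1/*T* | *N* = 11: 1/*N*, ratio | *N* = 10: 1/*N*, ratio |
|---|---|---|---|
| 1 | 100% | 9.1%, 11.0 | 10.0%, 10.0 |
| 2 | 50.0% | 9.1%, 5.5 | 10.0%, 5.0 |
| 3 | 33.3% | 9.1%, 3.7 | 10.0%, 3.3 |
| 4 | 25.0% | 9.1%, 2.8 | 10.0%, 2.5 |

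**Step 4. Denominator read literally.** If any postdose laboratory value qualifies a subject, the denominator is about *N* and the ratio about 1. The *N* − *T* subjects without a postdose lipase are then counted as not raised, so *x*/*N* is the incidence of detected raised lipase and only a lower bound on the true incidence.

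**Step 5. Comparison with glucose.** The SAP's stated reason for exempting nonfasting glucose is that a postdose grade cannot be called emergent when predose was mostly not measured. A subject in the first row of Step 1 is in that position for lipase.

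**The case against.** The strongest case on the other side has four parts.

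- **The inflation rests on a reading.** The denominator sentence does not say that the values must be for that test. This stands. The by-test layout makes the per-test reading the natural one, but a reader who takes the inflated rate as a settled feature of the SAP goes further than the text does.
- **Not everyone tested lacks a predose value.** Criterion 13 admits subjects with amylase above 1.5 × ULN, who would have a predose lipase and may be over-represented among those tested later. This stands too. A reader might infer that nearly every raised lipase is emergent by construction, or that only subjects whose amylase rises on treatment get a postdose lipase. The documents support neither: the share is 1 − *q*, and *q* is unknown.
- **The rule is cautious and transparent.** It comes from Protocol 8.6.3 and errs towards reporting a signal. Counts accompany percentages, and listings show every chemistry result, including the matching amylase. No formal laboratory testing is planned. Other rows may be sparse as well, since the fasting profile in Part 1 is scheduled only on Day 1. This limits the harm, but the row is still labelled wrongly.
- **Removing the label has a cost.** A subject with lower amylase at entry who develops raised amylase and lipase on treatment may be a true new case. This is fair, and it is why her result must stay visible by grade and in the listing.

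**Conclusion.** The point holds as an inconsistency in a stated rule. Lipase is put through a treatment-emergent classification that cannot be supported for subjects without a predose lipase, while the SAP declines that classification for nonfasting glucose because of the same gap. This follows from the text and needs no assumed counts.

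The size does need them. On the per-test reading, the percentage exceeds the whole-cohort figure by *N*/*T*, or 2.5- to 11-fold for 1 to 4 tested subjects in cohorts of 10 to 11. On the literal reading there is no such inflation, but untested subjects are taken as not raised. The share of raised values flagged by the missing-predose rule alone can lie anywhere from 0% to 100%.

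The effect is limited to one descriptive safety row in two small uncontrolled cohorts. It touches no efficacy result and no formal test. It is worth correcting because the row could mislead and the SAP already contains the remedy.

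**What to change.** Treat lipase as the SAP treats its other exceptions, in one of two ways:

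1. List it only, as for INR and prothrombin time, by marking its table label in Appendix 3 item 7 as not applicable.
2. Report maximum postdose lipase grade as a count, with the number reflex-tested and the cohort size both shown, and a footnote that subjects with amylase at or below 1.5 × ULN were not tested.

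In either case, make no treatment-emergent classification where predose lipase was not measured, and keep amylase as the tabulated pancreatic test. A bare percentage of the Safety Analysis Set would not be enough, because it is only a lower bound.

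SAP 7.2.2.2 should also say whether its denominator is test-specific. Because the lipase exception departs from Protocol 8.6.3, it should be noted in SAP 7.7.

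The cost is a sentence or two in SAP 7.2.2, one row of the label table and a line in 7.7, with no new data. The small downside is that a possible new-onset lipase rise without a predose value appears in the maximum-grade row or the listing, and not as treatment-emergent.

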### **7.3. Body Weight, Height, and Vital Signs**

Descriptive statistics will be provided by Cohort for vital signs and body weight as follows:

- Predose values
- Values at each postdose time point
- Change from predose at each postdose time point

Predose and postdose values will be defined as described in Section 3.8.1. Change from predose to a postdose visit will be defined as the postdose value minus the predose value. Body weight and vital signs measured at unscheduled visits will be included for the predose value selection.

In the case of multiple values in an analysis window, data will be selected for analysis as described in Section 3.8.3. No formal statistical testing is planned.

A by-subject listing of vital signs for the entire study (including Part 2) will be provided by subject ID number and visit in chronological order. In the same listing, a by-subject listing of body weight, height, and BMI will be provided.

### **7.4. Prior and Concomitant Medications**

#### **7.4.1. Antiretroviral Medications**

Any nonstudy ARV medications used prior to, during, or after the study (if collected) are all recorded on the ARV eCRF. All ARV medications recorded on the ARV eCRF will be coded using the Gilead-modified World Health Organization (WHO) Drug Dictionary for ARV medication. The WHO preferred name and drug code will be attached to the clinical database. All ARV medications recorded on the ARV eCRF will be listed. No inferential statistics will be provided.

#### **7.4.2. Concomitant Non-Antiretroviral Medications**

Concomitant non-ARV medications (ie, medications other than study drug that are taken while receiving study drug) will be coded using the WHO Drug Dictionary. The WHO preferred name and drug code will be attached to the clinical database. Use of concomitant medications from Part 1 first dose date to Part 1 last dose date and before Part 2 first dose date, whichever occurs earlier, will be summarized (number and percentage of subjects) by Cohort and preferred name. Multiple drug use (by preferred name) will be counted only once per subject. The summary will be sorted by decreasing order of total frequency.

If the start or stop date of non-ARV medications is incomplete, the month and year (or year alone, if month is not recorded) of the start or stop date will be used to determine whether the non-ARVs are concomitant or not. The medication is concomitant if the month and year of the start or stop (or year of the start or stop, if month is not recorded) of the medication does not meet either of the following criteria:

- The month and year of start of the medication is after Part 1 last dose date
- The month and year of stop of the medication is before Part 1 first dose date

If the start and stop date of non-ARV medications are complete, the start date is not after Part 1 last dose date and the stop date is not before Part 1 first dose date, or the non-ARV medications are marked as ongoing and start date is on or before Part 1 last dose date, the non-ARV medications are concomitant for Part 1 of the study.

Summaries of non-ARV concomitant medications will be provided for the Safety Analysis Set.

Subjects with any non-ARV concomitant medications during the study (including Part 2) will be listed. No inferential statistics will be provided.

#### **7.5. Electrocardiogram Results**

A shift table of the investigators' assessment of ECG results at each visit compared with predose values will be presented by Cohort using the following categories: normal; abnormal, not clinically significant; abnormal, clinically significant; or missing. The number and percentage of subjects in each cross-classification group of the shift table will be presented. Subjects with a missing value at predose or postdose will not be included in the denominator for percentage calculation. No inferential statistics will be provided.

A by-subject listing for ECG assessment results for the entire study including Part 2 will be provided by subject ID number and visits in chronological order.

#### **7.6. Other Safety Measures**

A by-subject listing of subject pregnancies during the study will be provided by subject ID number. No additional safety measures are specified in the protocol.

Although not necessarily related to safety, a by-subject listing of all comments received during the study on the comments form will be provided by subject ID number, and form for which the comment applies.

